4.3. Definitions, Computations, and Conventions

4.3.1. Definition of Date of First Dose and Date of Last Dose of Study Drug

The date of the first dose of study drug (relugolix or leuprolide) is defined as the date when a patient receives the first dose of study drug (the date of visit for injection of leuprolide acetate or the self-reported date of drug intake of relugolix by the patient). The date of the last dose of study drug is defined as the date a patient receives the last dose of study drug. If the date of last dose of study drug is unknown, the last date the study drug was known to have been taken will be used.

4.3.2. Study Day

Study day will be calculated with respect to the date of randomization (Study Day 1). For assessments conducted on or after the date of randomization, study day will be calculated as:

$$(\text{Assessment date} - \text{date of randomization}) + 1$$

For assessments conducted before the date of the randomization, study day will be calculated as:

$$(\text{Assessment date} - \text{date of randomization})$$

4.3.3. Definition of Treatment Duration

Treatment duration is defined as the duration of time from the date of the first dose of study drug to the date of the last dose of study drug as follows:

$$(\text{Date of last dose of study drug} - \text{Date of first dose of study drug}) + 1$$

For patients with partial or completely missing last dose of study drug, the following algorithm will be used to impute:

- If the last date of study drug is completely missing, the last known study drug taken date will be used as the last date of study drug;
- If the last date of study drug is partially missing
 - If only year YYYY is recorded, then impute this date: 31DECYYYY, if year = year of last known drug taken date and last date of study drug = minimum of (last known drug taken date, date of death, imputed date);
 - If both year and month are available, impute the missing day as the last day of the month and last date of study drug = minimum of (date of death, imputed date)

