6.1. Study Interventions Administered

Patients enrolled in this study were randomized 1:1 to receive oral relugolix 120 mg once daily with a loading dose of 360 mg on Day 1, or either leuprolide acetate 22.5 mg 3-M depot or 45 mg 6-M injection (plus first-generation anti-androgen for the first 4 weeks or longer if indicated in the opinion of the investigator).

As of 04 Dec 2023, enrollment in the MVT-601-056 study was halted and actively enrolled patients will be provided up to a 12-month clinical supply (relugolix or leuprolide acetate) based on their randomization assignment if they choose to remain in the discontinuation phase of the study. Amendment 1 of the protocol is provided for reference ([Appendix 5](#)).

Table 1: MVT-601-056 Study Interventions

Intervention Name	Relugolix	Leuprolide acetate 3-M or 6-M depot ^a or Leuprolide acetate injectable emulsion
Type	Drug	Drug
Dose Formulation	Tablet	Depot formulation
Dosage Levels	Loading dose: 360 mg (3 × 120 mg) Daily dose: 120 mg (1 × 120 mg)	22.5 mg or 45 mg (or 42 mg injectable emulsion)
Route of Administration	Oral	Subcutaneous or intramuscular
Use	Investigational medicinal product	Active comparator
Sourcing	Relugolix will be sourced and shipped direct-to-patient via a central pharmacy.	Leuprolide acetate will be sourced by the site to the patients.
Packaging and Labeling	Relugolix is provided in a bottle. Each bottle will be packaged and labeled as required for clinical study use.	Leuprolide acetate 22.5 mg 3-M or 45 mg 6-M depot injection used with standard of care packaging and labeling.

^a If an investigator prefers another dose regimen of leuprolide acetate this will require approval by the medical monitor.

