6.3. Randomization and Stratification

Eligible patients were assigned to one of two treatment groups in accordance with the randomization schedule using an Interactive Response Technology System. At baseline prior to the start of study intervention administration, each patient was randomized in Interactive Response Technology in a 1:1 ratio to one of 2 treatment groups (see [Table 2](#)).

Table 2: MVT-601-056 Treatment Arms

Treatment Arm	Randomized Treatment
Group A	Relugolix 360 mg (three 120 mg tablets) single oral loading dose on Day 1 followed by 120 mg orally once daily
Group B	Leuprolide acetate, 22.5 mg 3-M depot injection or Leuprolide acetate, 45 mg 6-M depot injection

Randomization was centrally stratified by the following factors using a permuted block method (see Section [4.1](#) for further details on the factors):

- MACE history (yes versus no);
- Age (≤ 65 versus > 65 years old);
- Presence of metastatic prostate cancer (yes versus no) (metastases in regional lymph node[s] are considered N1 and will, therefore, be stratified as non-metastatic).

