4.9. Prior Medications and Concomitant Medications

Prior medications and concomitant medications taken during the study treatment period will be summarized for all patients in the ITT population by treatment group. Medications are considered concomitant if exposure occurs during the treatment period (including use of enzalutamide, abiraterone, darolutamide, or apalutamide) while on study drug.

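### SAP treatment duration stops at the last leuprolide injection, so exposure is understated by up to one depot interval in that arm only

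*SAP*

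**What the plan says.** SAP 4.3.3 defines treatment duration for study drug in general, "from the date of the first dose of study drug to the date of the last dose of study drug as follows", and gives the formula (last dose date − first dose date) + 1. It has no term specific to an arm. Its imputation rules deal with missing or partial last-dose dates and do not add a dosing interval.

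SAP 4.3.1 supplies the dates. The first dose is "the date of visit for injection of leuprolide acetate or the self-reported date of drug intake of relugolix by the patient". For the end, "The date of the last dose of study drug is defined as the date a patient receives the last dose of study drug". For leuprolide that day is an injection visit.

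The two drugs are dosed very differently. Protocol 6.1 gives "oral relugolix 120 mg once daily with a loading dose of 360 mg on Day 1" in one arm and "either leuprolide acetate 22.5 mg 3-M depot or 45 mg 6-M injection" in the other. Protocol 6.3, Table 2, repeats the depot choice: "Leuprolide acetate, 22.5 mg 3-M depot injection or Leuprolide acetate, 45 mg 6-M depot injection". Table 1 in Protocol 6.1 also lists a 42 mg injectable emulsion, and its footnote adds: "If an investigator prefers another dose regimen of leuprolide acetate this will require approval by the medical monitor".

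SAP 5 is headed exposure and compliance but defines no exposure measure. SAP 4.9 refers to a treatment period without defining it: "Medications are considered concomitant if exposure occurs during the treatment period".

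**The concern.** The plus 1 in the formula credits the last dose with one day of treatment. That is right for a once-daily tablet. A depot is given to cover 3 or 6 months, so crediting the last one with a single day drops almost all of its interval. A patient who has one injection is recorded as treated for 1 day.

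The protocol itself treats the depot as relevant well beyond the injection date. The partner-pregnancy rule in Protocol 8.3.5 runs 3 months past the last 22.5 mg dose and 6 months past the last 45 mg dose, against 2 weeks for relugolix. That rule does not define exposure, but it shows a difference between products that the SAP formula ignores.

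Two outputs are at stake. First, any summary of duration by arm would show leuprolide patients as treated for less time than relugolix patients with the same cover. The gap would also vary within the leuprolide arm, because Protocol 6.2 lets the site choose the formulation. Second, if the treatment period in SAP 4.9 is programmed from the same dates, a medication first started after the last injection, while the depot is still active, would not count as concomitant in the leuprolide arm. The loss is fixed in days, so it weighs most on patients with few injections. Such patients are to be expected in a study that was stopped early.

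**Working it through.** The documents state no exposure figure, so there is none to reproduce. The check applies the SAP formula to on-schedule dosing.

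**Inputs**
- Formula: last dose date − first dose date + 1 (SAP 4.3.3).
- Last dose date for leuprolide: the injection day (SAP 4.3.1).
- Intervals: 3 months and 6 months (Protocol 6.1). The documents give no days. Assumed ranges are L = 84–91 days for 3-M and L = 168–183 days for 6-M.
- Relugolix interval: 1 day (Protocol 6.1).

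**Formulae.** With k injections at interval L:
- SAP duration = (k − 1)L + 1
- Time covered by depots = kL
- Shortfall = kL − [(k − 1)L + 1] = L − 1, whatever k is

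Only the last injection is undercounted. Earlier intervals are counted in full.

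**Shortfall in days**
- 3-M: 84 − 1 = 83 to 91 − 1 = 90
- 6-M: 168 − 1 = 167 to 183 − 1 = 182
- Relugolix: 1 − 1 = 0. For example, 365 daily doses give (365 − 1) + 1 = 365 days.

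**Share of covered time lost**

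| Product | Injections | SAP duration (days) | Covered (days) | Short by |
|---|---|---|---|---|
| 3-M | 1 | 1 | 84–91 | about 99% |
| 3-M | 2 | 85–92 | 168–182 | about 49% |
| 3-M | 4 (about 12 months) | 253–274 | 336–364 | about 25% |
| 6-M | 1 | 1 | 168–183 | about 99% |
| 6-M | 2 (about 12 months) | 169–184 | 336–366 | about 50% |
| 6-M | 4 (about 24 months) | 505–550 | 672–732 | about 25% |

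**Truncation.** If exposure ends before the last interval runs out, the shortfall is the time from the last injection to that end. Death 30 days after the last injection gives a shortfall of 30 days, not L − 1. The L − 1 figures are therefore upper bounds for each product.

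**The case against.** The strongest reply concerns consequence. The trial was discontinued, its one remaining objective is descriptive, and Protocol 9.1 rules out formal primary and secondary analyses. First-to-last-dose is a transparent measure of the dosing period, and the SAP does not call it drug coverage. No table named in the SAP uses it. All of this stands and limits the severity. It does not make the number comparable between arms once it is tabulated by treatment group.

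Three stronger readings are tempting.

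- **Inflated event rates.** A reader might infer that leuprolide event rates will be inflated, by 336/253 = 1.33 on 3-M or 336/169 = 1.99 on 6-M at about 12 months. The documents do not support this. SAP 6.1 plans numbers and percentages of patients, with no exposure-adjusted rate and no time at risk. Its treatment-emergent window for serious events runs from first dose to end of study and does not use treatment duration.
- **Concomitant medications certainly biased.** SAP 4.9 does not cite 4.3.3, so the link is an inference about how the undefined period will be programmed. Even on that reading, a drug already in use before the last injection still counts. Some later use may never be collected, because new medications come from the questionnaires (Protocol 6.5), which are not expected after transition to standard of care (Protocol 8.2.1).
- **A loss of 3 to 6 months for every patient.** This is the nominal maximum, less a day. It is smaller after death or a switch of ADT, and it may differ for the emulsion or another approved regimen.

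It would also be wrong to assume that the data for a repair are certainly in hand. Protocol 6.4 requires the dates of leuprolide administration to be recorded. No passage expressly says that the formulation given is recorded.

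**Conclusion.** The definition is wrong as written for a depot comparator, and no other section corrects it. Leuprolide duration is understated by up to one dosing interval less a day, while daily relugolix with a known last tablet date has no shortfall. The sizes rest on the assumed interval lengths, on-schedule injections and a last depot that runs its full interval.

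The consequence is limited to any exposure summary by arm and, conditionally, to the concomitant-medication classification in SAP 4.9. Planned adverse event counts and percentages are unaffected by the formula. Severity is minor to moderate: it is worth correcting before database lock because the repair is small, but no planned safety percentage depends on it.

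**What to change.** In SAP 4.3.3, define the end of exposure by arm:

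- Leuprolide: last injection date + labelled dosing interval of the product given − 1 day. List the interval for each product, including the 42 mg emulsion and any regimen approved by the medical monitor, because the documents do not state these.
- Truncate at the earliest of death, start of other ADT and end of data collection. Define the last of these as the patient's last study contact. Protocol 4.4 dates the end of study at the last injection for leuprolide, so truncating there would cancel the correction.
- Relugolix: keep the last tablet date.

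In SAP 4.9, state that the treatment period ends on this date. If the dosing-period measure is wanted as well, keep it under a separate label.

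The cost is a few lines of SAP text and one derived date, with no new visits and no change to patient care. There are two limits. The derivation assumes the nominal depot interval, and it needs the formulation at the last injection. The sponsor should confirm that this is recorded, or say how it will be obtained, before the SAP is finalised.

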4.3.4. Definition of Baseline Value and Post-Baseline Value

Unless otherwise specified, baseline values are defined as the last measurement before the first administration (date) of study drug. A postbaseline value is defined as a measurement taken after the first administration of study drug. Change from baseline is defined as (postbaseline value – baseline value).

4.4. Patient Disposition

The number and percentage of patients for each of the disposition (to be defined) categories will be summarized by treatment group for the ITT population. Reasons for discontinuation of study treatments and study will be collected and summarized in the study.

4.5. Screen Failure

Patients who consent to participate in the clinical study but are not subsequently entered in the study are considered to have had a screen failure. Number and percent of screen failure patients will be summarized.

4.6. Protocol Deviation

Protocol deviations will be categorized as important or minor per the study protocol deviation plan which will be established prior to patient enrollment of the study. Number and percent of patients with important protocol deviation will be summarized for the ITT population.

4.7. Demographics and Baseline Characteristics

Demographic and baseline characteristics will be summarized by treatment group for the ITT population. Categorical data will be summarized using frequencies and percentages, by treatment group and overall. Summaries of continuous data will display the mean, SD, median, minimum, and maximum. The numbers and percentages of missing values will also be summarized.

4.8. Medical History

Medical history will be coded using the Medical Dictionary for Regulatory Activities and will be summarized on ITT population by system organ class and preferred term (PT). A patient with multiple occurrences of medical history within a PT will be counted only once in that PT.

4.9. Prior Medications and Concomitant Medications

Prior medications and concomitant medications taken during the study treatment period will be summarized for all patients in the ITT population by treatment group. Medications are considered concomitant if exposure occurs during the treatment period (including use of enzalutamide, abiraterone, darolutamide, or apalutamide) while on study drug.

5. STUDY DRUG EXPOSURE AND COMPLIANCE

Following randomization, patients will follow SOC practices with their investigator, which for the leuprolide acetate group will include visits for injection of leuprolide acetate. The investigator must record all dates of leuprolide acetate administration in the electronic data capture system. For the relugolix group, patients will self-administer relugolix at home.

Each patient will have a follow-up visit (either in office or by telehealth; per the investigator's discretion) during this discontinuation phase until they transition to SOC.

6. SAFETY ANALYSES

Safety analyses will be performed on the safety population including summary of adverse event, serious adverse events, laboratory data, and vital signs.

6.1. Adverse Events and Serious Adverse Events

Per protocol, serious adverse events will be reported by the patient (or, when appropriate, by a caregiver, surrogate, or the patient's legally authorized representative) using questionnaires submitted electronically. Serious adverse events will also be reported by the investigators electronically through the electronic data capture.

The severity of all treatment-emergent adverse events will be evaluated by the investigator based on the National Cancer Institute's Common Terminology Criteria for Adverse Events (NCI CTCAE v5.0) and will be coded to preferred term and system organ class using the Medical Dictionary for Regulatory Activities 25.1 or higher.

Treatment-emergent serious adverse event is defined as any serious adverse event that occur after administration of the first dose of study drug and prior to the end of the study.

Serious adverse event summaries will be based on treatment-emergent adverse events, unless otherwise specified. Listing for all serious adverse events will be provided.

Tabular summaries with the number and percentage of patients with the following adverse events (but not limited to) will be provided:

- Overview of adverse events
- All adverse events
 - By system organ class and preferred term
 - By decreasing frequency of preferred term
 - By decreasing frequency of preferred term and relatedness to study drug

- All serious adverse events
 - By system organ class and preferred term
 - By decreasing frequency of preferred term
- Serious adverse events leading to study drug withdrawn
 - By system organ class and preferred term
 - By decreasing frequency of preferred term
- Serious adverse events in fatal outcome
 - By system organ class and preferred term
 - By decreasing frequency of preferred term

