4.4. End of Study Definition

The end of study is defined as the date of the last dispensation (last injection of leuprolide; last delivery of relugolix) before the patient transitions to SOC treatment.

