7.4. Patient and Study Completion

For an individual patient, study completion is defined as their last study communication at the end of the study (including any follow-up visits or telephone contact for determination of resolution of an adverse event).

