8.3. Adverse Events and Serious Adverse Events

Adverse events and serious adverse events will be reported by the patient (or, when appropriate, by a caregiver, surrogate, or the patient's legally authorized representative) using the questionnaires. The CRO is responsible for checking the questionnaires for selective safety data

(ie, serious adverse events and nonserious adverse events leading to treatment discontinuation) and for recording, reporting, and following up of these events.

Selective safety data will also be reported by the investigator.

All serious adverse event reporting is conducted in accordance with the Code of Federal Regulations Title 21 312.32.

8.3.1. Time Period and Frequency for Collecting Adverse Event and Serious Adverse Event Information

All adverse events and serious adverse events reported in the follow-up questionnaires will be collected from the signing of the ICF until the final study visit at the time points specified in the SoA (Section 1.3), irrespective of a causal relationship.

For serious adverse events and nonserious adverse events leading to treatment discontinuation reported in the follow-up questionnaires, the CRO is responsible to ensure these selective safety data are recorded and reported to the sponsor (or designee) within 5 calendar days of receipt unless there are suspected unexpected fatal or life-threatening serious adverse reaction reports, in which case they will be reported to the sponsor or designee within 2 business/3 calendar days, whichever is shorter, as indicated in [Appendix 2](#). The CRO will also submit any updated selective safety data to the sponsor as indicated in [Appendix 2](#).

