8.3.5. Pregnancy in Female Partners of Male Patients

The male patient should report a pregnancy in his female partner.

Details of all partner pregnancies in female partners who become pregnant (estimated date of conception) during the study or within 2 weeks after the last dose of relugolix 120 mg or 3 months after the last dose of leuprolide acetate 22.5 mg 3-M or 6 months after the last 45 mg 6-M depot injection will be collected after the start of study intervention if the female partner agrees to provide information through a Release of Information form.

If a partner pregnancy is reported, the investigator should inform the sponsor (or designee) within 8 calendar days of learning of the pregnancy and should follow the procedures outlined in [Appendix 3](#).

Protocol Amendment 2

Abnormal pregnancy outcomes (eg, spontaneous abortion, fetal death, stillbirth, congenital anomalies, ectopic pregnancy) are considered serious adverse events.

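### SAP 6.1 closes the treatment-emergent SAE window at an undefined end of study; on Protocol 4.4's definition (last injection or last drug delivery), the SAE summary tables omit events during the final supply

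*SAP*

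**What the plan says.** SAP 6.1 defines a treatment-emergent serious adverse event as "any serious adverse event that occur after administration of the first dose of study drug and prior to the end of the study". It adds that "Serious adverse event summaries will be based on treatment-emergent adverse events, unless otherwise specified" and that "Listing for all serious adverse events will be provided". The planned tables give numbers and percentages of patients, including tables for SAEs with fatal outcome and SAEs leading to study drug withdrawal. The SAP does not say when the study ends for a patient.

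Protocol 4.4, the one section headed as a definition of end of study, reads "The end of study is defined as the date of the last dispensation (last injection of leuprolide; last delivery of relugolix) before the patient transitions"; the transition meant is the move onto standard of care.

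Other passages point to a later date:
- Protocol 7.4: for an individual patient, "study completion is defined as their last study communication at the end of the study", which includes follow-up visits and telephone contact about adverse events.
- Protocol 8.3.1: events reported in the questionnaires "will be collected from the signing of the ICF until the final study visit".
- Schedule of Activities (Protocol 1.3), note c: the end-of-study visit can take place as standard of care begins.

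SAP 4.3.1 defines a date of last dose, but SAP 6.1 does not use it.

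**The concern.** Neither date in Protocol 4.4 ends exposure. After the last injection the depot has its whole interval still to run, and after the last delivery the tablets have yet to be taken. If a programmer combines SAP 6.1 with Protocol 4.4, the SAE tables lose events that occurred on drug and that the protocol collects.

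Describing safety is the only remaining objective (Protocol 3, SAP 1.1), and this definition decides which SAEs enter the main tables for it. Two of those tables are especially exposed. An SAE that kills the patient or ends his treatment also ends dispensing, so its onset normally falls after the last dispensation. Protocol 4.4 is framed around transition to standard of care and names no date for a patient who dies or withdraws. If the last dispensation is used for him too, the tables of fatal SAEs and of SAEs leading to withdrawal would omit the events they are meant to show, unless a further dispensation followed onset.

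SAP 6.1 also defines treatment emergence for serious events only. Nonserious events leading to discontinuation, the other category collected, have no window.

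**Working it through.** The plan gives no figure to reproduce on this point. The check combines the definitions and then works out how much on-drug time they leave.

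**Step 1, the literal window.** Start: first dose (SAP 4.3.1). End: last injection or last delivery (Protocol 4.4). The time lost for each patient is one final dispensing interval.
- One injection only: first dose and end of study fall on the same date, so the window is empty. The patient stays in the safety population (SAP 4.2.1), hence in the denominator, but cannot enter the SAE numerator.
- One relugolix delivery only: the drug is mailed to the patient, so the window closes before the first tablet.

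Short exposures are plausible. Consented patients could still be randomized after enrollment stopped (Protocol 5.3), and sites are to move patients to standard of care as soon as practicable (Protocol 4.1).

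**Step 2, inputs.** Leuprolide depots last 3 or 6 months (Protocol 6.1), taken as 90 and 180 days. Relugolix comes in 45-tablet bottles (Protocol 6.2), which is 45 days at one tablet daily. The number of bottles per delivery is not stated, so one (45 days) and two (90 days) are assumed. Each dispensation is assumed to fall when the previous supply ends. Total cover is set at 360 and 720 days for illustration. The supply of up to 12 months in the discontinuation phase comes on top of any earlier treatment.

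**Step 3, share of on-drug time kept** = (cover − last interval) / cover.

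| Last supply | 360 days of cover | 720 days of cover |
|---|---|---|
| Leuprolide 6-M (180 d) | 180/360 = 50% | 540/720 = 75% |
| Leuprolide 3-M (90 d) | 270/360 = 75% | 630/720 = 87.5% |
| Relugolix, 45-day delivery | 315/360 = 87.5% | 675/720 = 93.75% |
| Relugolix, 90-day delivery | 270/360 = 75% | 630/720 = 87.5% |

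Doubling the cover halves the gap between the 6-M depot and the 45-day delivery, from 37.5 to 18.75 percentage points.

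**Step 4, effect on a table, for 360 days of cover.** Expected percentage with an SAE = 1 − exp(−rate × days kept / 365.25). The same constant SAE rate is assumed in both arms. The documents give no rate, so three are shown, per patient-year.

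| Days kept | Rate 0.10 | Rate 0.20 | Rate 0.30 |
|---|---|---|---|
| 180 (6-M) | 4.8% | 9.4% | 13.7% |
| 270 (3-M or 90-day delivery) | 7.1% | 13.7% | 19.9% |
| 315 (45-day delivery) | 8.3% | 15.8% | 22.8% |
| 360 (full cover) | 9.4% | 17.9% | 25.6% |

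Every row falls short of full cover, and equal true risk can give unequal tabulated percentages.

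**Step 5, direction.** Against a 3-M depot the loss is equal at two bottles per delivery (2 × 45 = 90 days) and larger for relugolix at three (135 days). Against a 6-M depot it is equal at four bottles (180 days).

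**The case against.** The strongest reply is that the literal reading was not intended. SAP 6.1 does not cite Protocol 4.4. Protocol 7.4 and the end-of-study visit in the Schedule of Activities use the phrase for a later point, and an empty window after one injection is an implausible aim. Under Protocol 7.4, or a single study-wide date, the loss would mostly disappear. This stands as a description of the conflict. It does not remove the defect, because the SAP adopts neither reading and the one formal definition gives the wrong counts.

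A related reply is that note b of the Schedule of Activities collects questionnaires only until the end of study, so a literal reader would stop questionnaire collection at the last dispensation too. But Protocol 8.3.1 runs collection to the final visit, Protocol 8.2.1 expects questionnaires until transition to standard of care, and investigators also report SAEs. The note belongs among the passages to reconcile.

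Three stronger inferences are tempting, and the documents do not support them.
- *SAEs vanish from every summary table.* The restriction is stated for SAE summaries. The overview and all-adverse-event tables have no stated window, and all SAEs are listed.
- *The rule makes relugolix look worse.* That needs the 3-M/6-M mix, the delivery size and the time on drug. None is given, and the direction can reverse.
- *Protocol 8.3.5 shows that exposure lasts* "6 months after the last 45 mg 6-M depot injection". That section sets collection periods for partner pregnancy. It does not define exposure for adverse events.

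Finally, the analysis is descriptive in a terminated study, with no formal between-arm test. So reported frequencies are affected, not type I error or power.

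**Conclusion.** The definition is wrong as written. Taken with Protocol 4.4, it removes one final dispensing interval of on-drug time per patient from the SAE summaries. With the assumed intervals that is 12.5% to 50% of a 360-day exposure, 6.25% to 25% of a 720-day exposure, and all of a single-injection exposure. The omitted SAEs remain in the listing, so they are lost from the summaries and not from the report.

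The loss can differ by arm, but neither its size nor its direction can be fixed from the documents. The percentages with an SAE rest further on an assumed constant rate that is equal in the two arms. The conclusion itself needs no such assumption. It rests on Protocol 4.4 being the only formal definition of the term that SAP 6.1 uses, and on later passages that contradict it.

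**What to change.** In SAP 6.1, before database lock:
- Replace the reference to the end of the study with an explicit patient-level end date that covers the last dispensed supply and follows one rule in both arms. Use the patient's final study contact or end-of-study visit (Protocol 7.4 and 8.3.1), truncated at death, consent withdrawal or start of non-study ADT.
- Count events with onset on the day of death, so that fatal events are not cut by the truncation.
- Apply the same window to nonserious adverse events leading to discontinuation.

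Reconcile Protocol 4.4 with 7.4, and with note b of the Schedule of Activities.

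Do not borrow the periods in Protocol 8.3.5. They omit the 42 mg emulsion listed in Protocol Table 1 and may run past the collection period: questionnaires stop at transition (8.2.1), and investigators need not actively seek SAEs after participation ends (8.3.1.1).

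The cost is one SAP definition and one protocol clarification. No new data are needed, because Protocol 8.3.1 already collects events to the final visit and the proposed window ends no later than that contact.
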